### **3.5. Safety Endpoints**

See [Section 3.1](#).

## **4. ANALYSIS SETS**

### **4.1. Full Analysis Set (FAS)**

The full analysis set (FAS) will include all enrolled subjects with at least one dose of tofacitinib during this study.

### **4.2. Per Protocol Analysis Set**

Not planned.

### **4.3. Safety Analysis Set (SAS)**

The safety analysis set (SAS) will include all enrolled subjects with at least one dose of tofacitinib during this study. SAS is the same as FAS in this study.

### **4.4. Other Analysis Sets**

The sJIA1 analysis set consists all subjects in FAS with systemic JIA (sJIA). Both sJIA subjects from index studies A3921104 and A3921165 will be included in the sJIA1 analysis set.

The sJIA2 analysis set is a subset of sJIA1 analysis set. Only sJIA subjects from index study A3921165 will be included.

The pJIA analysis set consists all subjects in FAS with polyarticular course JIA (pJIA, i.e., extended oligoarthritis, polyarthritis RF+, polyarthritis RF-, systemic JIA with active arthritis but without active systemic features). The pJIA analysis set will not include subjects enrolled from index study A3921165.

The ERA analysis set consists all subjects in FAS with enthesitis-related arthritis (ERA).

The PsA analysis set consists all subjects in FAS with psoriatic arthritis (PsA).

## **5. GENERAL METHODOLOGY AND CONVENTIONS**

### **5.1. Hypotheses and Decision Rules**

There are no hypotheses since this study is an open--label single--arm long-term follow--up study with the primary and secondary objectives achieved through descriptive statistics.

Decision rules are not applicable since there are no formal hypotheses.

## 5.2. General Methods

In general, descriptive statistics will include number of subjects evaluated, number and percent for binary variables, and mean, standard deviation, minimum, 1st, 2nd (median) and 3rd quartiles and maximum for continuous variables. Graphics will be generated if needed.

## 5.3. Methods to Manage Missing Data

Missing data will not be imputed, and all analyses will be based on available data except Tanner Stage assessment and missing joint assessment. For Tanner Stage assessment, once a subject has reached the highest stage of development (Stage 5) then that score will be carried forward for the remainder of the study. More specifically, any missing Tanner Stage assessment after a Stage 5 score will be “imputed” with Stage 5, up to the next non-missing Tanner Stage assessment prior to study discontinuation. For missing joint assessment, the imputation method is provided in [Appendix 1.2](#)

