An interim analysis (data cutoff 04 Jun 2019, data snapshot 03 Jul 2019) was conducted for Study A3921145. At the time of the data cutoff, 227 subjects had enrolled in the study (signed informed consent), and 2 subjects from Study A3921104 were enrolled but not treated; 177 subjects were ongoing. Insufficient clinical response was the most common discontinuation reason to date. In general, available efficacy data of long-term treatment with tofacitinib showed stable improvement in JIA symptoms from baseline of the qualifying/index studies.

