7.1.6.1. JIA ACR Response Criteria

The assessments using JIA ACR 30, 50, 70, 90 and 100 will be performed. Other responder criteria may be assessed if appropriate. The JIA ACR 30, 50, 70, 90, 100 response criteria are as follows: 3 out of 6 JIA core set variables improved $\geq 30\%$, 50%, 70%, 90%, 100%, respectively, with no more than 1 out of 6 JIA core set variables worsened by $\geq 30\%$.

In subjects with systemic JIA, absence of fever due to sJIA in the preceding 7 days is also required (Ruperto et al. 2012).²² (see [Section 7.1.10.1](#)).

Applicable to Canadian Investigator Sites Only: The Investigator will calculate and record the subject's ACR30 response using ESR as the acute phase reactant at the Month 3 Visit and each subsequent visit thereafter. Subjects with less than an ACR30 response at 2 consecutive visits, beginning with the Month 3 visit and anytime thereafter, should be discontinued from study treatment, unless, in the opinion of the Investigator, it is in the subject's best interest to continue receiving tofacitinib (to be determined on a case-by-case basis and in consultation with the Sponsor). If continuation of treatment is warranted, the Investigator must contact the Sponsor to discuss the case and obtain prior approval.

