### 2.1.2. Secondary

- The secondary objective of this study is to evaluate the persistence of efficacy of tofacitinib for treatment of the signs and symptoms of JIA.

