## 6.2. Secondary Endpoints

All efficacy endpoints are secondary and listed in [Section 3.2](#). [Table 2](#) summarizes the analysis sets to be used in the analysis of each efficacy endpoint.

The secondary efficacy endpoints will be summarized using descriptive statistics by visit for the binary and continuous endpoints respectively. The percent (for the binary endpoints) and mean change (for the continuous endpoints) over time and associated standard errors will be plotted for analyses in sJIA1, sJIA2 and pJIA analysis sets (see [Table 2](#)).

The binary endpoints are JIA ACR responses, occurrence of JIA ACR disease flare, JIA ACR clinical inactive disease status and clinical remission, occurrence of JADAS minimum disease activity and inactive disease, eligibility of tapering, partial tapering success and complete tapering success for corticosteroids, MTX/leflunomide, and tofacitinib, absence of fever for sJIA subjects at each visit. Number, frequency, percent and the associated standard error will be presented for binary variables. JIA ACR disease flare will only be summarized for those who have reached Month 3 Visit of this extension study.

The continuous endpoints are change from baseline in physician global evaluation of disease activity, number of joints with active arthritis, number of joints with limitation of motion, CRP, ESR, CHAQ, JADAS-27 CRP, JADAS-27 ESR at each visit. Number, mean, standard deviation, standard error of the mean, median, quartiles, minimum, and maximum will be presented for continuous variables.

For ERA subjects, change from baseline in TEA, Modified Schober's Test, Overall Back Pain, Nocturnal Back Pain at each visit will be summarized as continuous variables.

For PsA subjects, change from baseline in BSA affected by psoriasis, PGA of psoriasis at each visit will be summarized as continuous variables.

For ESR and any efficacy endpoint summaries involving ESR, all ESR data points including those collected with expired/non-standard ESR kits will be used for analysis. Supportive analyses will be performed to evaluate the impact of expired/non-standard ESR kits (see Section 6.2.1).

For CHAQ and any efficacy endpoint summaries (i.e., JIA ACR responses, JIA ACR flare, and JADAS) involving CHAQ, subjects with invalid CHAQ measurements will be excluded for the visits where these invalid measurements were made. Examples of invalid CHAQ measurements include:

- incorrectly translated CHAQ data

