#### Appendix 1.3. JIA American College of Rheumatology (ACR) Response

The assessments using JIA ACR 30, 50, 70, 90 and 100 will be performed. Other responder criteria may be assessed if appropriate. The JIA ACR 30, 50, 70, 90, 100 response criteria (Giannini 1997) are as follows: 3 out of 6 JIA core set variables improved  $\geq 30\%$ , 50%, 70%, 90%, 100%, respectively, with no more than 1 out of 6 JIA core set variables worsened by  $\geq 30\%$ . Only ESR will be used to calculate ACR responses.

If the value in any of the components at a timepoint is missing, the component variables that are not missing will be used to determine the response status. As a general principle, if there are sufficient non-missing components to determine whether the JIA ACR endpoint is a response or non-response, then JIA ACR endpoint is not missing, else if the available non-missing components are not sufficient to determine the response status of JIA ACR endpoint then it is considered missing.

In order to avoid numerical difficulty, if the baseline value of any component is equal to 0, the following algorithm will be used in evaluating the percent change from baseline:

1. If change from baseline is also equal to 0, then percent change from baseline is set to be 0%;
2. If change from baseline is  $> 0$ , then percent change from baseline is set to be 999999%.

These percentages will be used to derive the JIA ACR endpoints. Change from baseline cannot be  $< 0$  since none of the components should have negative value.

In subjects with systemic JIA, absence of fever due to sJIA in the preceding 7 days is also required (Ruperto 2012). Note that here is different from index study A3921104 protocol, where only absence of fever due to sJIA is required (no requirement of timeframe).

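### By-visit efficacy percentages rest only on subjects with data at that visit, so exits for insufficient response could make efficacy look more persistent than it is

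*SAP*

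**What the plan says.** The secondary objective (SAP 2.1.2) is to "evaluate the persistence of efficacy of tofacitinib for treatment of the signs and symptoms of JIA". SAP 6.2 sets the display: "The secondary efficacy endpoints will be summarized using descriptive statistics by visit for the binary and continuous endpoints respectively", with percentages over time plotted for the sJIA1, sJIA2 and pJIA sets.

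The missing-data rule is in SAP 5.3: "Missing data will not be imputed, and all analyses will be based on available data except Tanner Stage assessment and missing joint assessment". The derivation appendices follow it. For JIA ACR response, "if the available non-missing components are not sufficient to determine the response status of JIA ACR endpoint then it is considered missing" (SAP Appendix 1.3), and flare uses the same handling (Appendix 1.4). A JADAS-27 score with any missing component is missing (Appendix 1.6). Flare takes Month 3 as its baseline and is summarised only for subjects who reached Month 3 (SAP 3.4.1 and 6.2).

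The tapering endpoints differ: their denominator is everyone who took the drug (SAP Appendix 1.8).

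On why subjects leave, Protocol 2.3.2 reports from the June 2019 interim: "Insufficient clinical response was the most common discontinuation reason to date". At Canadian sites, Protocol 7.1.6.1 has a treatment-stopping rule for "Subjects with less than an ACR30 response at 2 consecutive visits", with an exception where the investigator, in consultation with the sponsor, judges continuation to be in the subject's interest.

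The only supportive efficacy analysis (SAP 6.2.1) concerns expired or non-standard ESR kits. The only discontinuation table that the SAP specifies is the COVID-19 one (SAP 6.7).

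**The concern.** Under these rules a subject who loses response and leaves is a non-responder up to the last visit attended, and after that belongs to no category. If exit is related to response, the remaining denominator is enriched for responders, and the percentage can hold steady or rise while the enrolled cohort does worse. For flare the effect runs the other way on the scale but is equally favourable: a subject who flares and leaves is counted once and does not appear at later visits, and one who fails before Month 3 is never counted.

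The objective is about persistence, and a flat curve is what a reader would take as evidence of it. The misreading is foreseeable. The paragraph of Protocol 2.3.2 that names insufficient response as the leading reason for leaving also describes the available long-term data as stably improved. Protocol 9.5 and SAP 7 allow interim analyses for publication, so such curves may circulate before the final analysis. No planned efficacy output would show how far attrition accounts for the shape.

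**Working it through.** The plan states no figure for this point: there is no hypothesis test, and no response rates or counts by reason for leaving are given. The check therefore sizes the possible effect from the one retention figure available.

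**Inputs (Protocol 2.3.2, cutoff 04 June 2019).** 227 enrolled; "2 subjects from Study A3921104 were enrolled but not treated"; 177 ongoing. I assume that all 177 had been treated.

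**Leavers.** 227 − 2 = 225 treated. 225 − 177 = 48, and 48/225 = 21.3%. On all enrolled subjects: 50/227 = 22.0%.

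**Formula.** Let p be the displayed response rate among those remaining and s the share of the 48 who left for insufficient response. Counting those as non-responders and removing the other leavers from the denominator:

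rate = 177p / (177 + 48s)

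Both p and s are assumptions. At p = 0.80 the numerator is 141.6:

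- s = 0.25: 141.6/189 = 74.9%, 5.1 points lower
- s = 0.50: 141.6/201 = 70.4%, 9.6 points lower
- s = 1.00: 141.6/225 = 62.9%, 17.1 points lower

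Over a range of displayed rates:

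| Displayed p | s = 0.25 | s = 0.50 | s = 1.00 (bound) |
|---|---|---|---|
| 60% | 56.2% | 52.8% | 47.2% |
| 70% | 65.6% | 61.6% | 55.1% |
| 80% | 74.9% | 70.4% | 62.9% |
| 90% | 84.3% | 79.3% | 70.8% |

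**Attrition alone can raise the curve.** Suppose 65% of 225 respond (146.25 on average) and no subject ever changes status. If 24 non-responders leave, the observed-case rate is 146.25/201 = 72.8%. If 48 leave, it is 146.25/177 = 82.6%.

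**Limit of the illustration.** 177/225 is retention over the whole study at one calendar date. Entry was staggered and ongoing subjects had not all reached any given visit, so this fraction is not the retention behind any row of a planned table.

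**The case against.** The case for leaving the plan alone has several sound parts.

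- A reader might infer that efficacy is shown in completers only. It is not. Leavers contribute every visit attended, and the early-termination visit collects CHAQ, physician global, joints, CRP and ESR (Protocol 6.2.5), which SAP Appendix 1.12 assigns to a visit window by study day. A failing final visit is counted; what is lost is every visit after it. The tapering endpoints are not affected.
- A reader might infer that Canadian non-responders are removed automatically. The exception in Protocol 7.1.6.1 prevents that reading, and the number of Canadian subjects is not given.
- Many absences say nothing about efficacy. A3921103 and A3921104 subjects end participation after first pJIA approval (Protocol 3), and Protocol 1.1 already records US approval. Late entry, the Canadian 3-year limit and withdrawal at own request are further examples. Treating every absence as failure would over-correct.
- Some protection exists. SAP 6.2 tables give numbers with percentages, so shrinking denominators can be seen. Worsening of the underlying disease can be an AE (Protocol 8.3), and SAP 6.6 gives incidence rates for AEs leading to discontinuation. Protocol 9.2.2 allows exploratory analyses.
- The study is single-arm and descriptive, with safety as its primary objective. Observed-case data are a legitimate description of subjects who continue treatment.

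These points limit the size of the concern and the form of the remedy. They do not remove it. A shrinking N shows that subjects left, not why. An AE rate covers only exits recorded as AEs and sits among the safety results. An unspecified exploratory analysis commits the sponsor to nothing.

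**Conclusion.** The point holds as a risk of favourable bias in the by-visit response, flare, inactive-disease, remission and JADAS percentages when they are read as persistence in the enrolled cohort. The absence of any dropout-related efficacy analysis is certain from the SAP. The direction of bias is the expected one, given the leading reason for leaving. The size is not known.

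Two stronger readings are tempting. One is that non-response drives dropout and the curves are therefore inflated. The protocol says only that insufficient response was the most common reason as of June 2019; that can be well under half of exits, and the mix may have changed since. The other is to take 63% as the corrected value of a displayed 80%. That figure requires all 48 leavers to have left for insufficient response, which the protocol does not say; it is only the upper bound on the effect at that retention. A quarter to a half of leavers gives about 5 to 10 points at a displayed 80%, on assumed p and s.

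This affects interpretation of the secondary objective. Type I error and the primary safety objective are untouched. The change should be made because it is cheap, not because the study fails without it.

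**What to change.** Keep the observed-case display as planned. Add to SAP 6.2.1, by analysis set:

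1. A sensitivity percentage by visit for JIA ACR response, inactive disease and JADAS minimal and inactive disease, in which subjects who discontinued earlier for insufficient clinical response count as non-responders. The denominator is subjects who could have reached that visit, so it leaves out administrative exits (marketing approval, study closure, the Canadian 3-year limit) and subjects not yet at the visit. Exits for AE count as failure only in a separately labelled variant, since that is a different estimand. The SAP should also state how remaining exits, such as own request, are handled; treating them as missing matches the arithmetic above.
2. Cumulative incidence of discontinuation for insufficient response from first dose, with other exits as competing events, or censored if administrative. This also captures failures before Month 3.
3. Time to first flare after Month 3, with withdrawal for insufficient response counted as an event.
4. N at each visit printed under the plots.

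No new data collection should be needed: Protocol 6.2.6 already has the investigator ask the reason for withdrawal. The cost is additional tables and figures across up to five analysis sets, and response figures that will look less favourable than the observed-case ones.

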## 6. ANALYSES AND SUMMARIES

### 6.1. Primary Endpoints

The primary endpoints are standard laboratory safety data, adverse event (AE) reports, body weight, height and tanner stages. The Safety Analysis Set (SAS) will be used for analysis. For some endpoints, e.g., overall AE summary and AEs by SOC and PT, analyses will also be performed in sJIA2 analysis set and any additional summaries will be detailed in the programming plan.

All the safety data, including the following, will be summarized descriptively through appropriate data tabulations, descriptive statistics, and graphical presentations by visit:

- Adverse events will be summarized according to Pfizer standards.
- Safety laboratory tests will be summarized according to Pfizer standards.
- Subjects meeting certain cutoffs will be summarized for the following parameters: neutrophil counts, lymphocyte counts, serum creatinine levels, liver tests, lipid levels, hemoglobin.
- Subjects meeting discontinuation and monitoring criteria (see Protocol Appendix 8) will be summarized.
- Serious infections will be summarized.
- Incidence rate will be calculated for AEs of special interest. See Section [6.6](#) for details.
- For pubertal development as measured by Tanner Stage, a shift table of Tanner Stages from baseline to each post-baseline visit will be constructed by age group (2 to <6 years, 6 to <12 years, and 12 years or older) for males and females separately. The percentages in the shift table will be based on the number of subjects with available tanner stage data at both baseline and the post-baseline visit of interest.

- For assessment of growth as measured by body weight and height, a table of descriptive statistics for body weight and height standardized Z-scores (actual values and changes from baseline) at each visit will be constructed by age group (2 to <6 years, 6 to <12 years, and 12 years or older) for males and females separately.

Height (weight) Z-score is calculated using the following formulation:

$$Z = \frac{(X/M)^L - 1}{LS}, L \neq 0$$

Or

$$Z = \ln(X/M) / S, L = 0$$

where X is the physical measurement (e.g., height, weight) and L, M, and S are the values from standardized growth charts provided by the US Centers for Disease Control website (<http://www.cdc.gov/GrowthCharts/>) by gender for children from birth to 240 months. The Z-score cannot be calculated if age >240 months.

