2.3. Benefit/Risk Assessment

2.3.1. Risk Assessment

Safety concerns have been identified based on the totality of nonclinical and clinical data across the entire tofacitinib development programs (all indications) and/or are considered due to experience with other immunosuppressive agents. The nature and degree of the risk varies with the patient population; however, safety findings that may be associated with the use of tofacitinib include lipid elevations, decreases in hemoglobin, decreases in neutrophil and lymphocyte counts, increases in serum creatinine, increases in serum creatine kinase, infection risk, lymphoproliferative disorder/lymphoma risk, malignancy risk, non-melanoma skin cancer (NMSC), gastrointestinal perforations, viral reactivation, including herpes zoster, tuberculosis, cardiovascular (CV) disease, venous thromboembolism (VTE, manifested as pulmonary embolism and deep vein thrombosis), transaminase elevations, drug hypersensitivity and effects on pregnancy and the fetus. Interstitial lung disease (ILD) is also observed; ILD is a serious comorbidity for some populations in which tofacitinib has been studied and has been reported as a potential risk associated with other disease modifying anti-rheumatic drugs therapies.

Upon completion of a large randomized open-label post authorization safety surveillance (PASS) study in RA subjects who were 50 years or older with at least one additional cardiovascular (CV) risk factor, evaluating the safety profile of tofacitinib compared to TNF inhibitors, additional new potential risks for tofacitinib were identified. Those include Major Adverse Cardiovascular Events (MACE), myocardial infarction, lymphoma, lung cancer and fractures.

As per the European Medicines Agency (EMA) Pharmacovigilance Risk Assessment Committee (PRAC) conclusion to a recent safety signal assessment on the data from this study (EPITT 19382), myocardial infarction, lung cancer and lymphoma are categorized as important identified risks and malignancy excluding NMSC continues to be categorized as an important potential risk in the context of the EU risk management plan and EU Summary of Product Characteristics. Recommendations for use of the marketed product (Xeljanz [tofacitinib]) in the EU were also adopted by PRAC, advising healthcare professionals that tofacitinib should only be used in patients over 65 years of age, patients who are current or

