6.2.6. Subject Withdrawal

Guidelines for monitoring and discontinuing subjects from this study are listed in [Appendix 8](#). If a subject is discontinued for safety reasons an Early Termination Visit should be conducted whenever possible.

If venous thromboembolism is confirmed, discontinue treatment with tofacitinib and withdraw the subject from the study ([Appendix 8](#), Guidelines for Monitoring and Discontinuation).

All abnormal laboratory events of clinical significance should be followed until the laboratory values have returned to normal or baseline level or are deemed clinically stable. In addition, any subject with a confirmed increase in serum creatinine $>33\%$ above the

average of screening and baseline values, will be followed up with retesting every one to two weeks until the creatinine elevation has fully reversed to within 10% of the average of screening and baseline values or has stabilized.

Subjects may withdraw from the trial at any time at their own request/or request of their parent or legal guardian, or they may be withdrawn at any time at the discretion of the investigator or sponsor for safety or behavioral reasons, or the inability of the subject to comply with the protocol-required schedule of study visits or procedures at a given study site.

If a subject does not return for a scheduled visit, every effort should be made to contact the subject and parent/legal guardian. In any circumstance, every effort should be made to document subject outcome, if possible. The investigator should inquire about the reason for withdrawal, request the subject to return all unused investigational product(s), request the subject to return for a final visit, if applicable, and follow-up with the subject regarding any unresolved adverse events (AEs).

If the subject withdraws from the study, and also withdraws consent for disclosure of future information, no further evaluations should be performed, and no additional data should be collected. The sponsor may retain and continue to use any data collected before such withdrawal of consent.

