9.1. Sample Size Determination

Sample size will be determined by the number of subjects who enroll from the qualifying/index studies. Feedback from literature and Investigators indicates about 90% of subjects from qualifying/index studies would enter into this study. Therefore, approximately 340 subjects are expected to join from currently planned studies (ie, A3921103, A3921104 and A3921165). Enrollment will depend on the timing of the initiation of on-going and planned studies. Analyses performed, including interim analyses, if any, will primarily be for safety though some measures of efficacy may be analyzed, and no adjustment of sample size due to interim analyses is needed (No hypothesis testing is planned in this study).

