Herpes zoster (shingles) is a painful rash that develops on one side of the face or body. The rash consists of blisters that typically scab over in 7 to 10 days. Before the rash appears, people often have pain, itching, or tingling in the area where it will develop. This may happen several days before the rash appears. Most commonly, the rash occurs in a single stripe around either the left or the right side of the body. In other cases, the rash occurs on one side of the face. Shingles on the face can affect the eye and cause vision loss. In rare cases (usually in people with weakened immune systems), the rash may be more widespread on the body and look similar to a chickenpox rash. Other symptoms of shingles can include: fever, headache, chills, and upset stomach.

Appendix 17. Summary of Changes from Original Protocol through Amendment 11

Document	Version Date	Summary of Change
Protocol Amendment 11	26 May2021	
Global Amendment
 
Protocol is amended as follows:
 
 • Protocol summary Section 3 study design: end of study text updated to clarify that subjects participation to the A3921145 study will end in 2 phases. • Schedule of Activities and Study Procedures Section 6.2.5 updated to clarify which procedures are required at the End of Study/Early Termination visit. • Addition of monitoring criteria related to Creatinine and Lipids increase for continuous assessment of subject's safety in the Appendix 8. • Creatinine discontinuation criteria wording updated in Appendix 8 to require two sequential increases in serum creatinine >50% over the average of screening/baseline and a confirmed creatinine clearance (CrCl) decrease of >30%. These updates are made to account for potential increases in creatinine due to physical activity, age and growth. CrCl added to the schedule of activities footnote and Section 7.2.9 laboratory tests. • Exclusion criterion #27 related to history of allergies, intolerance or hypersensitivity to lactose or CP-690,550 (tofacitinib): This country-specific exclusion criterion is made global to ensure consistent eligibility criteria for the study population. • Exclusion #8 is updated such that any infection requiring hospitalization, parenteral antimicrobial therapy or

090177e19a2c798c\Approved\Approved On: 18-May-2022 13:36 (GMT)

Document	Version Date	Summary of Change

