### **3. ENDPOINTS AND BASELINE VARIABLES: DEFINITIONS AND CONVENTIONS**

#### **3.1. Primary Endpoints**

- Incidence of clinical laboratory abnormalities and change from baseline in clinical laboratory values;
- Incidence and severity of adverse events;
- Validated assessments of growth (body weight and height) and pubertal development (Tanner Stage of Development);
- Incidence of abnormalities in physical examination;
- Incidence of vital sign abnormalities and change from baseline in vital sign measures;

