### 3.4. Baseline Variables

#### 3.4.1. Definition of Baseline

Baseline will be defined in the following way for all statistical analyses except for JIA ACR disease flare, and safety monitoring and discontinuation:

- First determine the number of off-study days (enrollment gap) between the last visit date in the qualifying study and the first visit date in this extension study.
- If the gap is  $\leq 14$  days, the baseline value will come from the baseline value of the qualifying study, if available. If it is not available, the baseline value will be missing.
- If the gap is  $> 14$  days, use the following decision tree to determine which baseline value, from the qualifying study or from this extension study, will be utilized in the analyses.

Qualifying Study Baseline Available [a]	Extension Study Baseline Available [b]	Baseline Value for Use in Analyses, if Gap $> 14$ days
No	No	No Baseline (Missing)
No	Yes	Extension Study
Yes	No	Qualifying study
Yes	Yes	Extension study

[a] The baseline values from the qualifying study with a randomized withdrawal design (i.e., A3921104 and A3921165) will come from the open-label period baseline.

[b] The baseline values from this extension study will come from 1) separate screening and baseline visits after EOS visit of the qualifying study, 2) a combined screening/baseline visit after EOS visit, or 3) a screening/baseline visit combined with the EOS visit. More specifically, extension study baseline will be the last non-missing assessment on or before Day 1 and prior to first dose of study drug administration in this extension study. Only data collected in the extension study database will be used. If a baseline value is not available by design (i.e., not planned to be collected at screening or baseline visit according to the protocol), extension study baseline availability will be “No” in the above decision tree.

For JIA ACR disease flare, baseline values will be from Month 3 visit of this extension study regardless of the gap calculated above.

For baseline definitions for use in safety monitoring and discontinuation, please see A3921145 protocol Appendix 8.

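### The planned by-visit change in raw serum creatinine mixes growth with drug effect; SAP 6.1 should add a height-based eGFR summary by age group

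*SAP*

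**What the plan says.** SAP 3.1 lists as a primary endpoint "Incidence of clinical laboratory abnormalities and change from baseline in clinical laboratory values". The reference for that change is set in SAP 3.4.1: "Baseline will be defined in the following way for all statistical analyses except for JIA ACR disease flare, and safety monitoring and discontinuation". The result is one value per subject. It comes from the index study when the enrolment gap is 14 days or less, and normally from the extension when the gap is longer.

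SAP 6.1 presents the safety data by visit, with laboratory tests following the sponsor's standards. For creatinine it adds only this: "Subjects meeting certain cutoffs will be summarized for the following parameters: neutrophil counts, lymphocyte counts, serum creatinine levels". The cutoffs are not stated. The same section breaks height, weight and Tanner stage down by age group and sex, and converts height and weight to Z-scores. Creatinine gets none of this.

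Protocol 2.3.1 names creatinine among the findings that may go with the drug: "increases in serum creatinine, increases in serum creatine kinase". Appendix 17 gives the reason for Amendment 11's change to the creatinine criteria: "These updates are made to account for potential increases in creatinine due to physical activity, age and growth". That change added a CrCl condition to Appendix 8. SAP versions 3 and 4 post-date the amendment, but neither adds a growth-adjusted creatinine summary.

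**The concern.** Subjects enter at 2 to <18 years, and the visit schedule runs to Month 120. A healthy child's creatinine rises as the child grows, so a table of change from an entry value drifts upward with follow-up whether or not the drug affects the kidney. There is no control arm to show how much of the drift is growth.

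Two misreadings follow. A rise caused by growth may be reported as a creatinine effect of a drug already suspected of one. A modest true fall in filtration may also be dismissed as growth. The sponsor accepted the mechanism when it amended Appendix 8, but the correction did not reach the SAP's change-from-baseline summary.

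**Working it through.** The documents give no expected creatinine rise, so there is no plan figure to reproduce.

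**Inputs from the documents.** Bedside Schwartz: eGFR = 0.413 × Ht/Scr (Protocol Appendix 5, item 1). CrCl under 12 years: K × Ht/Scr, with K = 0.70 for boys and 0.55 for girls. CrCl from 12 years: (140 − age) × weight/(72 × Scr), × 0.85 if female (Appendix 5, item 2). Age bands: SAP 6.1.

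**Assumed inputs (not in the documents).** Median heights of 87, 115, 150 and 170 cm at 2, 6, 12 and 18 years, with straight lines between and no growth after 18. Entry ages are spread evenly within each band. eGFR is constant.

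**Step 1: growth-only rise.** With eGFR constant, Scr(t)/Scr(0) = Ht(t)/Ht(0). Example for entry at 4 years:
- Height at entry: 87 + 2 × 7 = 101 cm.
- At 7 years: 115 + 35/6 = 120.8 cm, and 120.8/101 = 1.196, or +19.6%.
- At 9 years: 132.5 cm, and 132.5/101 = 1.312, or +31.2%.

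Band averages:

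| Entry age | 3 years | 5 years | 3 / 5 years, growth 30% slower |
|---|---|---|---|
| 2 to <6 | +20% | +31% | +14% / +22% |
| 6 to <12 | +12% | +18% | +8% / +13% |
| 12 or older | +5% | +6% | +3% / +4% |
| 2 to <18 | +11% | +17% | +8% / +12% |

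At 1 year the all-ages average is about +4%, or about +3% with slower growth. Years run from the baseline value. For subjects with a gap of 14 days or less that is the index-study baseline, so more time has passed than the extension visit label shows.

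**Step 2: sensitivity to growth shape.** Straight lines smooth out the pubertal spurt. With assumed year-by-year heights, a boy entering at 12 goes from 149 to 170 cm in 3 years (+14%), and a girl from 151 to 162 cm (+7%). The figure for 12 or older is therefore low for boys at the bottom of that band.

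**Step 3: Appendix 8.** Its creatinine criteria need a rise >50% or ≥0.5 mg/dL and also a CrCl fall >30%. Under age 12, K × Ht/Scr does not change with growth at constant eGFR, so growth alone cannot meet the pair.

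**Step 4: why the protocol's CrCl is unsuitable for the trend.** At age 12 the equation changes, and the units go from mL/min/1.73 m² to mL/min. Scr cancels from the ratio of the two equations. At 149 cm and 40 kg (assumed):
- Boy: (128 × 40/72)/(0.70 × 149) = 71.1/104.3 = 0.682, a fall of 32%.
- Girl: (128 × 40 × 0.85/72)/(0.55 × 149) = 60.4/81.95 = 0.738, a fall of 26%.

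From 33 to 50 kg the apparent fall runs from 44% to 15% for boys and from 39% to 8% for girls, with no change in function.

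**The case against.** The strongest reply is that growth is already handled where it matters. SAP 6.1 tabulates subjects meeting the Appendix 8 criteria, which carry the CrCl condition. SAP 6.6 gives incidence rates for renal events, including the acute renal failure SMQ. The study is descriptive: "No hypothesis testing is planned in this study". The sponsor's reporting standards, which are not in these documents, may use age-specific ranges. All of this stands, and it limits the point to the change-from-baseline display and possibly the undefined cutoffs. It does not remove the drift from that display, which is a primary endpoint.

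A reader might infer more from Protocol 6.2.6, which sets a follow-up rule for a confirmed rise above 33% in raw creatinine, namely that growth alone would push young subjects over a primary-analysis threshold. The documents do not support that. The rule governs retesting, continuing "until the creatinine elevation has fully reversed to within 10% of the average of screening and baseline values or has stabilized". It is not in Appendix 8, and the SAP never tabulates it. Nor do the undefined cutoffs in SAP 6.1 have to be relative to baseline.

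Long-horizon projections are also weak. Subjects from A3921103 and A3921104 leave after the first pJIA approval, which Protocol 1.1 already reports. Only 177 of 227 enrolled subjects were ongoing at the June 2019 cutoff. The number of young, long-stay subjects is not given.

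**Conclusion.** The point holds for the by-visit change in raw creatinine. At constant kidney function that table would show a mean rise of about +11% at 3 years and +17% at 5 years across entry ages 2 to <18, and about +20% and +31% for entry at 2 to <6. Subjects followed for only about a year are little affected. The sizes rest on assumed heights and an even spread of entry ages. The direction rests only on the protocol's equation and the fixed baseline.

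It would go too far to say that the renal safety question cannot be answered from the planned output. The Appendix 8 summary is exposed only through the equation change at age 12, and the renal-event rates are not exposed to growth. The documents give no expected size for a drug effect on creatinine, so its size relative to the drift cannot be judged. This is an inexpensive improvement that should be made before the tables are interpreted.

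**What to change.** In SAP 6.1:
- Add by-visit actual value and change from baseline in bedside-Schwartz eGFR (Appendix 5, item 1). Use one equation throughout, for visits before age 18, with height and creatinine both taken at the SAP 3.4.1 baseline.
- Present it by the existing age groups (2 to <6, 6 to <12, 12 or older), with the number of subjects whose eGFR falls by more than 30%. This count is a descriptive tabulation, not a management threshold.
- Keep the raw creatinine change and read it alongside the eGFR table. State the creatinine cutoffs.
- Do not use the protocol's CrCl for this trend, because of the break at age 12.

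The cost is SAP wording and one derived variable. The height Z-scores already require height at baseline and at each visit, and creatinine is in every safety panel. The documents set no upper age for the equation. The limit at 18 is a choice made here, and it leaves adult visits on raw creatinine.

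Separately, Protocol 6.2.6 (raw creatinine) and Appendix 8 (creatinine plus CrCl) apply different creatinine rules, and the text does not say how they relate. The sponsor should reconcile them; no clinical threshold is proposed here.
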